3. PARTICIPANT SELECTION AND ENROLLMENT PROCEDURES

Refer to the Participant Eligibility Checklist in Appendix A.

3.1 Inclusion Criteria

- 3.1.1 Be female and have a diagnosis of BC (Stage I-III).
- 3.1.2 Be scheduled for planned cancer treatment (e.g. chemotherapy or biologics such as herceptin).
- 3.1.3 Have at least 6 weeks of cancer treatment (e.g. chemotherapy or biologics such as herceptin) remaining.
- 3.1.4 Be at least 21 years of age.
- 3.1.5 Be able to understand written and spoken English.

Behavioral Intervention for Insomnia in Cancer

- 3.1.6 Report sleep disturbance of 8 or greater on the ISI, and report insomnia that began or got worse with diagnosis of cancer or treatment with chemotherapy (to exclude pre-existing, chronic insomnia).
- 3.1.7 Have a Karnofsky score ≥ 70 to ensure that patients are able to participate in intervention and assessments.

3.2 Exclusion Criteria

MUST NOT have a documented or self-reported, current diagnosis of any of the following conditions that would make it unsafe or impossible to adhere to the study protocol &/or endorse the last criterion

- 3.2.1 /Unstable self-reported medical or psychiatric illness (Axis I – current or within the last 5 years) that would make it unsafe or impossible to adhere to the study protocol
- 3.2.3 Substance abuse or dependence or met criteria within past year
- Sleep apnea or restless leg syndrome (RLS)
- 3.2.5 Are unable or unwilling to discontinue anxiolytics within 4 hours of education sessions

3.3 Informed Consent Process

All participants must be provided a consent form describing the study with sufficient information for participants to make an informed decision regarding their participation. Participants must sign the IRB approved informed consent prior to participation in any study specific procedure. The participant must receive a copy of the signed and dated consent document. The original signed copy of the consent document must be retained in the medical record or research file.

3.4 Randomization Procedures

Participants will be randomized into one of two arms: BBT-I or HEAL. The study data manager will use a computerized random number generator to assign participants into arms. In order to keep study blinded from assessors, only the interventionist providing the intervention, the data manager, and the clinical intervention supervisor will know randomization.

3.5 Study Timeline

Primary Completion:

The study will reach primary completion 48 months from the time the study opens to accrual.

Study Completion:

The study will reach study completion 60 months from the time the study opens to accrual.

4. TREATMENT PLAN

Breast Cancer Patients: We will recruit our participants from the Stanford Women's Cancer Center utilizing clinician and support group referrals as we have done in our pilot study. The PI is the Director of Cancer Survivorship Research Program at Stanford Medical Center, and our team has an ongoing relationship with all of the breast medical oncologists at Stanford. [name] is the Medical Director of Stanford University Cancer Center and Co-Investigator on the study. During the breast cancer disease management group meetings and tumor board, new cancer patients are discussed and evaluated by [name] and the study's personnel for eligibility for the study. The first step, as with all protocols in our lab, is to identify potentially eligible patients via our center's electronic medical records system (EPIC). In the present study, at or around the time of the patient's first chemotherapy treatment, approval will be sought from the patient's oncologist to invite patients who meet the preliminary eligibility criteria to participate in the study. We also have ongoing support from the Breast Cancer Connections' (BCC) Advocacy Task Force. The BCC sees several hundred breast cancer patients and survivors annually and has agreed to continue referring new patients to this study.

Procedures: During the consent process, all study subjects will be screened for eligibility by research staff at Stanford University. By signing the consent form, participants will grant permission to obtain their cognitive test data from another source (such as another research study or clinical testing) for this study if they do not complete the neuropsychological testing portion in this study. Participants will undergo four assessments (~one hour each) at baseline, post-treatment (6 weeks), and 6-month (30 weeks), and 12-month (58 weeks) follow-ups. During each of the assessments, participants will wear a heart rate monitoring device (Bodyguard Firstbeat®) that records heart rate variability for 10 minutes at each assessment point. Heart rate variability data will not be collected from a participant if she has an implanted device for heart failure (e.g., pacemaker, defibrillator, left ventricular assist device, etc.). Study participants will be asked to maintain a daily sleep diary for 7 days at baseline, post intervention, 6-month follow-up and 12-month follow-up. Patients will also be requested to wear an actigraph on their wrist (Actiwatch 64®, MiniMitter) for 7 days at baseline, post intervention, and follow-ups, and collect saliva for 2 days at each assessment point. Participants will collect saliva starting 2 days prior to their chemotherapy appointments to avoid interaction with corticosteroids. The RA responsible for assessment will make follow-up calls at each assessment point to each participant to promote compliance, prompt completion, and assess potential side effects of the behavioral interventions. In addition, participants will be asked to provide a small amount of blood (approximately 1-2 tablespoons) at each assessment.

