2.3 Rationale

Background: Sleep disturbance, particularly insomnia, is prevalent in cancer patients undergoing chemotherapy. Our preliminary data show that our novel intervention, Brief Behavioral Therapy for Insomnia (BBT-I), significantly reduces insomnia in breast cancer patients receiving chemotherapy. BBT-I is modeled on standard cognitive behavioral therapy for insomnia (CBT-I), including both stimulus control and sleep scheduling, and has been successfully modified to make it more suitable for breast cancer patients undergoing adjuvant or neoadjuvant chemotherapy with recently developed insomnia symptoms. Our preliminary research suggests that BBT-I is an acceptable and feasible intervention for insomnia in breast cancer patients that might also lead to improvement in fatigue and cognitive difficulties.

Methods: This research is designed to determine the efficacy of the BBT-I in comparison with the attention-matched behavioral control in reducing insomnia, fatigue, and cognitive difficulties in breast cancer patients. In addition, this study will examine the potential involvement of moderators (age, depression, anxiety, and hot flashes), specific behavioral mechanisms (maladaptive sleep behaviors, dysfunctional beliefs and attitudes), and physiological mechanisms (dysregulated circadian rhythms, disrupted wake-sleep cycles, and autonomic tone) as potential mediators of intervention-related changes in insomnia and the secondary outcomes of fatigue and cognitive difficulties. To address these aims, 180 breast cancer patients with acute insomnia during chemotherapy treatment will be recruited and randomized to receive either BBT-I or a behavioral control focused on Healthy Eating Education Learning. Each intervention condition will consist of 2 face-to-face sessions + 4 phone calls, delivered over a period of six weeks.

Behavioral Intervention for Insomnia in Cancer

Assessments will include sleep diaries, questionnaires, neuropsychological testing, actigraphy, heart rate variability measurement, blood draw, and salivary cortisol collection at baseline, post-intervention, and 6- and 12 months follow ups. By offering this intervention during chemotherapy when patients are just beginning to develop insomnia, we hope to alleviate and avoid the development of chronic insomnia in the survivorship phase.

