4.3 Alternatives

The patient may elect not to participate as an alternative to this study. They will continue to receive their normal care. During informed consent, we will describe our behavioral interventions, study procedures and questionnaires. We will inform our participants about potential risks despite their being minimal. We anticipate that a small proportion of our participants might potentially experience mild discomfort implementing BBT-I procedures (They might experience daytime fatigue and/or sleepiness, and/or memory and concentration difficulties). We will also inform them of the limits in confidentiality, because the intervention may take place in an open area in the ITA if absolutely necessary. We do not have an alternative treatment.

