7. ADVERSE EVENTS AND REPORTING PROCEDURES

7.1 Potential Adverse Events

BBT-I may result in temporary increases in daytime fatigue and/or sleepiness, and/or memory and concentration difficulties. Blood drawing may cause pain and bruising at the site where the blood is taken, and sometimes, it causes people to feel light-headed or even to faint. Rarely people might get an infection at the site of the needle stick. Heart rate monitor electrodes and the gel used to attach them may cause a skin reaction.

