7.2 Adverse Event Reporting

Adverse events will be graded according to CTCAE v4.03. Both Serious and Non-Serious Adverse Events will be clearly noted in source documentation and listed on study specific Case Report Forms (CRFs). The Protocol Director (PD) or designee will assess each Adverse Event (AE) to determine whether it is unexpected according to the Informed Consent, Protocol Document, or Investigator's Brochure, and related to the investigation. All Serious Adverse Events (SAEs) will be tracked until resolution, or until 30 after the last dose of the study treatment.

SAEs CTCAE Grade 3 and above, and all subsequent follow-up reports will be reported to the Stanford Cancer Institute Data and Safety Monitoring Committee (DSMC) using the study specific CRF regardless of the event's relatedness to the investigation. Following review by the DSMC, events meeting the IRB definition of 'Unanticipated Problem' will be reported to the IRB using eProtocol within 10 working days of DSMC review, or within 5 working days for deaths or life-threatening experiences.

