9. STUDY CALENDAR

	Baseline	Post Intervention	6 Month Follow-up	12 Month Follow-up
On Study Data (Demographic and clinical data)	X			
Clinical Record Information (Clinical data)	X			
Demographic Questionnaire/Medication	X			
Insomnia Severity Index (ISI)	X	X	X	X
Brief Fatigue Inventory (BFI)	X	X	X	X
Hopkins Verbal Learning Test (HVLT)	X	X	X	X
Clinical Assessment of Depression (CAD)	X	X	X	X
Mobile Cognitive Assessment Battery (MCAB)	X	X	X	X
Comprehensive Trail Making Test (CTMT)	X	X	X	X
Controlled Oral Word Association Test (COWAT)	X	X	X	X
Heart Rate Variability	X	X	X	X
Blood Draw	X	X	X	X
Actigraphy	1 week	1 week	1 week	1 week
Saliva Collection	X	X	X	X
Sleep Behavioral Self Rating Scale (SBSRS)	X	X	X	X
Pittsburgh Sleep Quality inventory (PSQI)	X	X	X	X
Dysfunctional Beliefs about Sleep (DBAS)	X	X	X	X
Difficulties in Emotion Regulation Symptoms (DERS)	X	X	X	X
European Organisation for Research and Treatment of Cancer (EORTC) Quality-of-Life-Questionnaire-C30	X	X	X	X
Godin Leisure Time Exercise Questionnaire (GLTEQ)	X	X	X	X
Reduced Home Ostberg Morningness Eveningness Questionnaire (rMEQ)	X	X	X	X
Nutrition Knowledge Questionnaire (NKQ)	X	X		
Sleep Diaries	1 week	1 week	1 week	1 week
Daily Diaries	1 week	1 week	1 week	1 week
BBT-I/HEAL Checklists		6 times during intervention		
Feedback	X	X		

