10.1.4 Measurement Time Points

Baseline, 6 weeks, 6 months and 12 months.

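### The plan writes in no side-effect enquiry between baseline and week 6, when the named harms of BBT-I are most naturally expected, so they may be under-detected

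*Combined protocol and SAP*

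**What the plan says.** **The expected harms.** Section 7.1 states: "BBT-I may result in temporary increases in daytime fatigue and/or sleepiness, and/or memory and concentration difficulties". The other risks listed there come from the blood draw and the heart-rate electrodes. Section 4.3 repeats the same symptoms and ties them to the activity of treatment: "We anticipate that a small proportion of our participants might potentially experience mild discomfort implementing BBT-I procedures". Neither section gives an onset time or a duration.

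**The enquiry.** Section 4 (Procedures) has the research assistant responsible for assessment make "calls at each assessment point to each participant to promote compliance, prompt completion, and assess potential side effects of the behavioral interventions". The same section schedules "four assessments (~one hour each) at baseline, post-treatment (6 weeks), and 6-month (30 weeks), and 12-month (58 weeks) follow-ups", and Section 10.1.4 confirms the time points as "Baseline, 6 weeks, 6 months and 12 months".

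**The treatment period.** Section 2.3: "Each intervention condition will consist of 2 face-to-face sessions + 4 phone calls, delivered over a period of six weeks". The Study Calendar (Section 9) lists BBT-I/HEAL checklists "6 times during intervention". The plan does not describe what these checklists contain.

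**The recording rule.** Section 7.2: "Both Serious and Non-Serious Adverse Events will be clearly noted in source documentation and listed on study specific Case Report Forms (CRFs". Events are graded by CTCAE v4.03. The section does not say who asks, when, or over what recall period.

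**The concern.** The plan names a specific set of short-lived harms and separately states when side effects will be asked about. The two do not line up. The harms are most plausible while women are following the sleep prescription in weeks 0 to 6, and the enquiry schedule has no point inside those weeks.

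The named harms are also worsening in the domains where Hypothesis 2 (Section 12.5) expects improvement: fatigue and cognitive difficulties. A rise in fatigue that appears and resolves before week 6 would leave no trace in the fatigue and cognitive measures, which follow the four assessment points, and it might not reach the safety data either. A low count of side effects in the trial report could then reflect when people were asked rather than what happened.

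Spontaneous report is a weak substitute in this setting. Section 2.3 cites cancer-related fatigue in 70% to 100% of patients on chemotherapy, so a woman may not think to attribute extra tiredness to the study. The contacts also differ by arm: BBT-I sessions discuss insomnia and fatigue, while HEAL sessions discuss nutrition (Section 5.1). Volunteered reports could therefore differ between arms, in either direction, for reasons unrelated to harm.

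**Working it through.** The plan states no figure on this point, so there is none to reproduce. The check is of the schedule, followed by an illustration on assumed values.

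**Schedule**
- Side-effect enquiries (Section 4): weeks 0, 6, 30 and 58. The week-0 enquiry precedes treatment and cannot detect its effects.
- Gaps between enquiries: 6 − 0 = 6 weeks, 30 − 6 = 24 weeks, 58 − 30 = 28 weeks.
- Enquiries strictly between week 0 and week 6: none.
- Contacts during treatment (Section 2.3): 2 + 4 = 6 in each arm. The plan mentions a side-effect question at none of them.

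**Other instruments.** In the Study Calendar, the fatigue inventory, cognitive tests, symptom questionnaires, sleep diaries and daily diaries follow the assessment points. The feedback questionnaire after treatment is described in Section 10.1 as asking whether the intervention helped. The only record scheduled within treatment is the checklist, whose content is not given.

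**How much could be lost (assumed values, not in the documents).** Suppose onset is uniform over weeks 0 to 6, the effect lasts *D* weeks (*D* ≤ 6), nothing is volunteered, and a resolved effect is recalled at the week-6 call with probability *r*. Then

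share captured = *D*/6 + (1 − *D*/6) × *r*.

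For example, *D* = 1 and *r* = 0.5 gives 0.167 + 0.833 × 0.5 = 0.583.

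| Duration *D* | *r* = 0 | *r* = 0.5 | *r* = 0.9 | *r* = 1 |
|---|---|---|---|---|
| 1 week | 17% | 58% | 92% | 100% |
| 2 weeks | 33% | 67% | 93% | 100% |
| 3 weeks | 50% | 75% | 95% | 100% |
| 6 weeks | 100% | 100% | 100% | 100% |

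The loss runs from none to most of the events, depending on two quantities the documents do not give. The table shows what the answer depends on; it does not estimate the loss.

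**The case against.** The strongest reply is that the finding reads silence as absence. Section 7.2 covers all adverse events, serious or not, and is not limited to assessment points. Every woman has six conversations with study staff in six weeks. The checklist may already contain a side-effect item. The week-6 call comes at the end of treatment, has side effects as a stated purpose, and nothing confines it to current symptoms. Effects still present at week 6 would be reachable by that call and by the fatigue and cognitive measures. Section 4.3 expects only a small proportion of women to be affected, and mildly. Hypothesis 2 runs through 12 months, so an early, passing rise in fatigue would not contradict a later benefit.

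Much of this stands, and it rules out three stronger readings that a reader might infer:
- *That the trial will under-detect these harms.* With good recall at week 6, or an item already on the checklist, little or nothing is lost. The documents support only that under-detection may occur.
- *That nobody asks anything during treatment.* The plan does not say so. It leaves the matter unstated.
- *That the number of women missed can be given.* There is no incidence in the documents, so any count would be invented.

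The point about 12 months also stands: this is a gap in harm detection, not a bias in the efficacy comparison.

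The reply does not close the gap. Section 7.2 governs what happens to an event once it is known and sets nobody to elicit it. Section 4 does state when side effects are asked about, and that schedule skips the treatment weeks.

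A second objection concerns the remedy. Sections 3.4 and 12.1.1 say the interventionist knows the allocation while assessors are blinded. Moving the questions to the treatment contacts risks unequal ascertainment in the very table they are meant to fill. That is a real cost, and the fix has to deal with it.

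**Conclusion.** The concern holds as a possibility of under-detection. The only written enquiry skips the period in which the plan's own named harms are most naturally expected. Effects that resolve before week 6 depend on being volunteered, or on recall over an unstated period. The magnitude cannot be derived from the documents.

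The conclusion rests on two inferences. The first is that the effects arise mainly during weeks 0 to 6; Section 4.3's link to carrying out the procedures supports this, but no onset window is stated. The second is that the checklist does not already ask about side effects; if it does, what remains is to say so and to state the recall period. The remedy is cheap enough to justify without knowing the size of the loss.

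**What to change.** 1. Add two scripted, participant-reported items to the BBT-I/HEAL checklist: new or worse daytime fatigue or sleepiness, and new or worse memory or concentration difficulty. Word them identically and ask them at all six contacts in both arms.
2. Grade the answers as Section 7.2 already provides, and tabulate them by arm for weeks 0 to 6.
3. State in Section 4 that the week-6 call covers the whole period since baseline.
4. Keep the assessment research assistant's enquiry as the blinded check on what the interventionists record. This relies on Sections 3.4 and 12.1.1; Section 2.4 describes the study as open and should be reconciled with them.

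**Cost.** Two items on a form already scheduled six times per participant, roughly a minute per contact, and one safety table. More low-grade events will be recorded in both arms, against a high background of chemotherapy fatigue, so a small excess under BBT-I may still be hard to separate. Recording by someone who knows the allocation can distort the comparison; fixed wording and the blinded call limit this but do not remove it. The intervention and the assessment schedule are unchanged.

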4.1 General Concomitant Medication and Supportive Care Guidelines

The study permits patients to remain on medications prescribed as part of their treatment regimen. We are excluding patients on daily sleep medications for our clinical trial. Our study procedures and intervention are supportive care only. They are an add-on to their clinical care for breast cancer.

4.2 Criteria for Removal from Study

Patients can be removed from the study if they experience disease progression that requires extended hospitalization or experience symptoms that make participation in the study difficult or impossible (e.g., development of psychosis, extreme pain, nausea). Participants are free to

withdraw at any time if the treating oncologist deems withdrawal necessary or if the patient decides to withdraw for any reason. All of our participants are receiving the behavioral interventions in addition to their usual care.

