12.4.2. Analysis Plan

For our primary Hypothesis 1, we will examine whether the BBT-I group will show more improvement, compared to the attention control group for insomnia symptoms measured by ISI from baseline to the 12-month follow-up. The group comparison will be made in line with the

Behavioral Intervention for Insomnia in Cancer

intention to treat principle. We will analyze the data using mixed effects (growth curve) modeling^{89,90} fully utilizing outcome data repeatedly measured four times for most participants (baseline, 6, 30, and 58 week). For estimation of mixed effect models, maximum likelihood (ML) estimation will be used. For ML estimation of these models, the Mplus program version 7.11 or above will be used.⁹¹ Data points that are missing due to subject attrition will be handled assuming that data are missing at random⁹² conditional on observed information, which is less restrictive than missing completely at random⁹² assumed in fixed effects analyses such as ANCOVA and regression analysis. In this procedure, all available cases including the ones with missing information will be included in the analyses. By including every subject who completed at least one assessment, we are not only more likely to conserve power, but also less likely to produce biased effect estimates. Given the sample and baseline covariates we will be collecting, we believe mixed effects modeling using ML is a reasonable approach. Nonetheless, we will conduct additional analyses at least for key hypotheses as a form of sensitivity analysis. For this purpose, we will apply the multiple imputation approach⁹³ utilizing various auxiliary variables in the data. We will conduct additional analyses allowing for some deviation from MAR, for example assuming MAR conditional on intervention adherence status.⁹⁴⁻⁹⁷

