12.5.1 Analysis Population

All patients contributing both baseline measurement and 12-month follow up will define the efficacy population.

Missing data

In our primary analytical strategy, we proposed to employ the statistical analysis method widely known as the mixed effects modeling approach using the maximum likelihood (ML) estimation. The use of mixed effects modeling is critical in implementing the intention-to-treat principle and therefore maintaining the validity of our inferences in the presence of missing data. Data points that are missing due to attrition and nonresponse will be handled assuming that data are missing at random (MAR¹⁰⁰), conditional on observed information. We would like to emphasize that our method is less restrictive and therefore less likely to result in bias and misleading conclusions than alternative procedures utilizing missing completely at random (MCAR¹⁰⁰), assumed in fixed effects analyses such as ANOVA and regression analysis. In analyses utilizing MCAR, cases with missing information are simply excluded from the computations. By including every participant who completes at least one assessment in the analysis utilizing MAR, we are not only more likely to conserve power, but also less likely to produce biased effect estimates. Given the sizable sample and baseline covariates assessed, we believe mixed effects modeling using ML is a reasonable approach. Nonetheless, we are aware that the assumption of missing at random conditional on observed information can be somewhat violated in practice (because we cannot possibly collect every variable related to the missing data). To address this concern, we will conduct additional analyses at least for the key hypotheses (1 & 2) as a form of sensitivity analysis. For this purpose, we will apply the multiple imputation approach¹⁰¹ utilizing various auxiliary variables in the data. Additionally, we will conduct sensitivity analysis allowing for some deviation from MAR, for example assuming MAR conditional on intervention adherence status.^{97,102-104}

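### Section 4.2 allows removal from the whole study without securing later ISI, which can create outcome-related missing data that the planned analyses do not specifically target

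*Combined protocol and SAP*

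**What the plan says.** Section 4.2 (Criteria for Removal from Study) gives two grounds. The first: "Patients can be removed from the study if they experience disease progression that requires extended hospitalization". The second applies to women who "experience symptoms that make participation in the study difficult or impossible", with psychosis, extreme pain and nausea as examples. The same section also provides for withdrawal by the woman herself or when her oncologist thinks it necessary. It does not separate leaving the sessions from leaving the assessments, and no section says whether the ISI is collected after removal.

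Both interventions run for six weeks. The ISI is due at baseline and at weeks 6, 30 and 58 (sections 9, 10.1.4 and 12.4.2). Sections 12.4.2 and 12.6.2 put the main comparison at week 58. Section 10.1 names the 6-month change instead, but the present point applies at either time.

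On analysis, section 12.4.2 says "The group comparison will be made in line with the" intention-to-treat principle. Section 12.5.1 adds: "The use of mixed effects modeling is critical in implementing the intention-to-treat principle". On missing data it says: "Data points that are missing due to attrition and nonresponse will be handled assuming that data are missing at random". The model takes in anyone with one or more assessments ("By including every participant who completes at least one assessment in the analysis utilizing MAR"). Section 12.5.1 concedes that this assumption may fail to some degree. It therefore plans multiple imputation with auxiliary variables, and an analysis that departs from missing at random, with conditioning on adherence as its only example. The same section also states: "All patients contributing both baseline measurement and 12-month follow up will define the efficacy population".

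**The concern.** Progression, extended hospitalization and severe symptoms plausibly go with worse sleep; sections 2.2 and 2.3 themselves link insomnia to progression, fatigue and treatment symptoms. If a woman is removed when such an event occurs, her ISI after the event is not seen. The mixed model then predicts her week-58 value from visits before she worsened. Calling the comparison intention to treat does not restore those outcomes.

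The timing sharpens this. For an event after week 6 there is no session left to stop, so removal mainly ends follow-up. At stake is the validity of the week-58 arm difference if removal works unequally between arms, and some precision if it does not. A removed woman without a 12-month visit would also fall outside the efficacy population defined in 12.5.1.

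**Working it through.** **1. The plan's own power figure.** Section 12.6.2 gives power 0.88 to 0.99 for d = 0.4 to 0.6, with 90 per arm, two-sided alpha 0.05, a linear trend, reliability 0.6 and 25% attrition by 6 months.

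- Re-derivation: a linear growth mixed model with visits at weeks 0, 6, 30 and 58, equal baseline means, random-intercept variance 0.6, residual variance 0.4 (total SD 1), and no random-slope variance.
- Retention: 1 / 0.90 / 0.75 / 0.75. The 10% loss at week 6 and no further loss after 6 months are assumptions; the plan gives neither.
- Standard error of the week-58 arm difference: 0.1286 SD. Power = Φ(d/SE − 1.96). At d = 0.4: 0.4/0.1286 − 1.96 = 1.15, power 0.88. At d = 0.6: about 1.00. The stated range is reproduced to within rounding and model choice.

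**2. Precision cost if removal is equal by arm.** The same model with no attrition has standard error 0.1115 SD. At d = 0.4: 0.4/0.1115 − 1.96 = 1.63, power 0.95. Attrition of all kinds therefore costs at most 0.95 − 0.88 = 0.07 in power. Removal under 4.2 is an unstated share of that. Both figures depend on the random-intercept form: with random-slope variance of 0.1 to 0.6, power at d = 0.4 with the planned attrition falls to 0.82 to 0.58.

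**3. Bias in the arm difference.** Let p be the share removed in an arm and δ the amount by which their unseen week-58 ISI is worse than the model predicts. The BBT-I benefit is overstated by

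p_B·δ_B − p_C·δ_C

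where B is BBT-I and C is control; a negative value means the benefit is understated. The documents give neither p nor δ, so every line below is an illustration under assumed inputs.

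| Assumed removal and departure | Bias | Share of effect |
|---|---|---|
| Equal p and equal δ in both arms | 0 | 0% |
| 5-point gap in p, δ = 3 ISI points in both arms | 0.05 × 3 = 0.15 points | 0.15/2.0 = 8% |
| 10-point gap in p, δ = 6 ISI points in both arms | 0.10 × 6 = 0.60 points | 0.60/2.0 = 30% |
| p 10% v 5%, δ = 1 SD in both arms | 0.05 SD | 0.05/0.4 = 12.5% |
| p 15% v 5%, δ = 1 SD in both arms | 0.10 SD | 0.10/0.4 = 25% |
| p 25% in both arms, δ = 1 SD v 0.5 SD | 0.125 SD | 0.125/0.4 = 31% |

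The 2.0-point effect is d = 0.4 times an assumed SD of 5. The last row shows that equal removal rates are not enough: the link to later ISI must be equal too.

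**4. Do the planned safeguards reach this mechanism?**

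- Multiple imputation helps as far as the auxiliary variables carry the event. Fatigue, depression and quality of life are scheduled at all four visits (section 9), and current treatment is recorded at each assessment (section 10.1). If assessments stop at removal, these stop as well. Clinical record data are listed at baseline only. Serious adverse event records (7.2) may catch some hospitalizations, but that tracking is limited in time.
- Conditioning on adherence concerns the six-week intervention. It does not describe progression or illness after week 6.
- Section 4.2 does not ask for the date or reason of removal, which an analysis aimed at these women would need.

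**The case against.** Much can be said for the plan, and several stronger readings are not supported.

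- **That 4.2 ends ISI collection.** A reader might infer this, but the text is permissive and silent on later assessments. The gap is that nothing secures the data, not that a rule forbids collecting them. Consent pages were not available for review.
- **That the analysis cannot repair the loss.** Missing at random covers whatever observed ISI explains, imputation may recover more, and the plan acknowledges that its assumption can fail. What stands is that neither sensitivity analysis names removal for progression or symptoms.
- **That BBT-I side effects will drive removal.** Section 7.1 says "BBT-I may result in temporary increases in daytime fatigue and/or sleepiness, and/or memory and concentration difficulties". These effects are temporary, section 4.3 expects mild discomfort in a small proportion, and none is among the examples in 4.2. Section 5.1 also relaxes the sleep advice on sick days. An arm difference is possible, not shown.
- **That the bias figures are estimates.** They are not. Pilot attrition was about 8% from all causes (12.5.1). At 1:1 allocation, a 10-point gap within 8% overall would need 13% v 3%, and a 5-point gap 10.5% v 5.5%, with every loss a removal. The planning figure of 25% leaves more room but is also all-cause.
- **That power is lost for no reason.** Section 4.2 gives reasons, and 12.6.2 already allows for 25% attrition.

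It is also fair that some women in hospital or with psychosis could not answer a questionnaire, so not all outcomes can be recovered. That limits the gain but does not explain why those who could answer should be lost.

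**Conclusion.** The point holds in a limited form. The removal rule covers the whole study, follow-up runs 52 weeks beyond the sessions (58 − 6), and no section secures the ISI after removal. This can produce outcome-related missing data that the primary model may not fully correct and that the planned sensitivity analyses do not specifically address.

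The documents do not establish any bias in the arm difference. It is zero when removal and its consequences are equal by arm. The illustrative 0.15 to 0.6 ISI points rests wholly on assumed removal gaps, departures and SD, and its direction depends on which arm loses more. The precision cost cannot exceed the gap between 0.88 and 0.95 in power at d = 0.4 under the random-intercept linear model. This is a worthwhile, inexpensive improvement rather than a flaw that invalidates the trial.

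**What to change.** In section 4.2, separate stopping the sessions from stopping outcome collection:

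- When a removal criterion is met or sessions stop, continue at least the ISI at whichever of the week 6, 30 and 58 assessments remain, by Qualtrics or phone, for women able and willing to answer, unless consent to follow-up is withdrawn.
- Reconcile this with the oncologist-directed withdrawal wording in the same section, so that it is clear whether that ends the sessions, the assessments or both.
- Record the date and reason for each stop, and tabulate them by arm.

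The clinical grounds for stopping are left to the protocol. The cost is a short change to 4.2, a check that the consent wording covers continued follow-up, and a few extra questionnaires. The ISI has seven items, Qualtrics is already in use, and assessment calls are already planned. The downside is the small added burden, and some women will be too ill to reply.
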